4. SELECTION AND ENROLLMENT OF PARTICIPANTS

Primary care clinics

The OCHIN Lead Co-Investigator will collaborate with the HealthPartners Co-PIs to identify eligible service areas (groups of related clinics) that will be randomized 1:1 to the CI-CDS or UC treatment group. OCHIN will enroll at least three service areas with at least 10 total constituent primary care clinics as CI-CDS replication sites; a similar number of service areas and primary care clinics will serve as usual care (UC) replication sites. Stratified randomization by SA size may be used to balance the number of constituent clinics in each treatment group. Replication site clinics must currently have access to cardiovascular (CV) Wizard to be eligible for randomization. Service areas were chosen as a unit of randomization to avoid intervention contamination within groups of these highly related clinics.

CI-CDS and UC service areas will be approached for participation in the study. Service areas, and their constituent clinics, that agree to participate by allowing full or silent implementation of the CI-CDS system will be considered enrolled.

Recruitment will be conducted by the OCHIN study team, with support as needed from the HealthPartners staff. Eligible service areas and their clinics will be sent an introductory recruitment email with relevant study-related information, such as outlining the goals of the study, the CI Wizard tool, and an invitation to participate. Study team staff will follow-up via email, telephone, or video conference platform to answer any questions, provide demos of CI Wizard CDS, and/or share additional information regarding participation with service areas that are interested, as appropriate.

Once a service area agrees to participate, OCHIN will follow up with a Memorandum of Understanding (MOU) that outlines participation expectations, a timeline for study activities, and details regarding compensation. These MOUs will be signed by OCHIN and leadership at the participating service areas prior to starting study activities. Service areas will receive an impact payment of up to \$3000 as compensation for the time spent engaging in study activities. This impact payment will be distributed by OCHIN and is provided to the service area and not to any individual within the service area or clinic.

4.3 Study Enrollment Procedures

The clinician survey will not be conducted at the replication site and thus any survey-related procedures are not applicable.

5. STUDY INTERVENTIONS

5.1 Interventions, Administration, and Duration

At the replication site, the CI-CDS user interface will only be operative in intervention service areas that are approached and agree to fully implement the CI-CDS. The CI-CDS will run invisibly

in the background in all enrolled service areas. Having the CI-CDS run invisibly at all study sites ensures that study and intervention eligibility are assessed identically for all patients with visits at all study clinics in all enrolled service areas. See **Section 9.2** of this appendix for more information about randomization procedures.

CI-CDS user interface functionality may vary slightly between service areas within the replication site, such as differences in quick order availability and region-specific patient resource materials. For example, if quick orders are not feasible in some service areas, a static recommendation to place an order may be implemented instead.

The CI-CDS tool will function similarly at the replication site and the primary site, with OCHIN's EHR securely exchanging data with the HealthPartners web service at every encounter of adult patients aged 65 or older. The OCHIN EHR data securely exchanged via the HealthPartners web service will initially be saved in an operational repository at HealthPartners. Limited EHR and Wizard use data will then be securely transferred and stored in a research repository at HealthPartners used for study purposes using a random study ID to reduce the risk of breach of confidentiality. See **Section 10** of this appendix for more information on data that will be stored in this research repository.

5.4 Adherence Assessment

Print rates by rooming staff at replication site clinics will be measured and grouped by clinic and clinician but will not be reported monthly to clinic leadership.

6. STUDY PROCEDURES

6.1 Schedule of Evaluations

Health care claims databases (e.g., paid amounts for emergency room visits or inpatient stays) are not available to be utilized at the replication site.

6.2. Description of Evaluations

6.2.5 Clinician surveys

The clinician survey will not be conducted at the replication site and thus these procedures are not applicable.

6.2.6 Chart audits

Chart audits will not be conducted at the replication site and thus these procedures are not applicable.

6.2.7 Patient / caregiver dyad interviews

Interviews will not be conducted at the replication site and thus these procedures are not applicable.

7. SAFETY ASSESSMENTS

7.1 Specification of Safety Parameters

Clinicians at replication site clinics can use the Feedback Tab to let the OCHIN team know of any questions or potential errors in the CDS. The OCHIN team will triage any feedback received through the Feedback Tab and communicate to the HealthPartners team if appropriate.

7.2. Methods and Timing for Assessing, Recording, and Analyzing Safety Parameters

Surveillance of information stored in the Wizard repository will be used to monitor safety events at the replication site.

7.3 Clinician Feedback and Safety Events

7.3.1 Clinician Feedback

Use of the Feedback Tab at replication site clinics will generate an email that is sent to the OCHIN study team members. The OCHIN team will communicate any feedback received through the Feedback Tab to the HealthPartners Team, when appropriate. The study teams will then discuss this feedback and any necessary actions, and reply to the clinician to answer the question, discuss steps taken to address the issue, or gather additional information if needed to further troubleshoot.

7.3.2 Safety events

Due to limitations in availability of data for emergency department visits, hospitalizations, and deaths at the replication site, we are unable to monitor these safety events at this site. We will measure suicide attempts as a safety event at the replication site.

9. STATISTICAL CONSIDERATIONS

9.2 Sample Size and Randomization

Operational considerations at the replication site make clinic-randomization impractical. To accommodate these considerations, randomization will be conducted by service area rather than clinic. Service areas eligible for randomization are those that currently have access to CV Wizard.

9.2.1 Treatment Assignment Procedures

All eligible service areas will be randomized 1:1 to CI-CDS intervention or Control to maximize the likelihood that CI-CDS and UC service areas are similar on observed and unobserved characteristics. Service areas may be stratified based on number of clinics to ensure a balanced number of clinics between intervention and control groups. Service areas in the intervention group will be approached to participate in the study, which includes turning on the CI-CDS user interface. If they do not agree, they will be invited to turn on the CI-CDS invisibly to collect data in the background. CI-CDS service areas that agree to either of these options will be considered enrolled. Service areas randomized to UC that agree to run the CI-CDS invisibly in the background will be considered enrolled.

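### Replication service areas are asked to join only after randomisation, with a heavier first request in the CI-CDS arm, so outright refusals can unbalance the enrolled arms

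*Protocol*

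**What the plan says.** The order of events is set in the replication appendix (Protocol Section 15.5), appendix Section 9.2.1. Allocation comes first: "All eligible service areas will be randomized 1:1 to CI-CDS intervention or Control", and the stated reason is "to maximize the likelihood that CI-CDS and UC service areas are similar on observed and unobserved characteristics". The approach follows. For the intervention arm, "Service areas in the intervention group will be approached to participate in the study, which includes turning on the CI-CDS user interface". There is a fallback: "If they do not agree, they will be invited to turn on the CI-CDS invisibly to collect data in the background", and "CI-CDS service areas that agree to either of these options will be considered enrolled". For the control arm, "Service areas randomized to UC that agree to run the CI-CDS invisibly in the background will be considered enrolled".

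Appendix Section 4 agrees with this order. Areas already carry their arm label when contacted ("CI-CDS and UC service areas will be approached for participation in the study"), count as enrolled only once they agree, and sign a memorandum of understanding (MOU) after agreeing. It also gives the planned size: "OCHIN will enroll at least three service areas with at least 10 total constituent primary care clinics as CI-CDS replication sites", with a similar number for UC.

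Appendix Section 10 says that replication data are gathered through the CI-CDS tool; no other source is described. The appendix gives no expected refusal rate, no comparison of enrolled with refusing areas and no replacement rule. SAP Section 2.1 leaves replication randomisation, outcome measurement and analysis to a site-specific supplement that is not among the documents.

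**The concern.** Randomisation makes the arms comparable as allocated. It does not protect a comparison of the areas that remain after each has learned its arm and decided whether to take part, least of all when the two arms were first asked for different things. An area asked to adopt a visible tool may disengage altogether where the same area, asked only for background data collection, would have agreed. UC areas may also refuse, for other reasons.

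An area that refuses everything contributes no outcome data, so analysing by intention to treat cannot bring it back. If refusal is related to how readily an area already diagnoses cognitive impairment, the replication estimate carries a bias that the outcome model cannot remove. The number of randomised units is small, so one refusal can matter. At the primary site, by contrast, Protocol Section 3 describes health-system leaders as having agreed to enrol clinics into the randomised trial.

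**Working it through.** **1. What each arm must accept to be enrolled (appendix Section 9.2.1)**

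| | CI-CDS arm | UC arm |
|---|---|---|
| First request | take part with the interface on | run silently |
| If declined | invited to run silently | no further offer described |
| Minimum to be enrolled | silent running | silent running |
| Not enrolled, no data | refuses both | refuses silent running |

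The minimum commitment is the same in both arms; the first request is not. Declining the interface and refusing everything therefore have different consequences.

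**2. The plan's own replication figure**

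Inputs (Protocol Section 9.2.2, median assumptions): 26 clinics, 60 patients per clinic, ICC 0.04, UC rate 8%, power 0.80, two-sided alpha 0.05.

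- Design effect = 1 + 59 × 0.04 = 3.36.
- Effective sample size per arm = (26 × 60 / 2) / 3.36 = 780 / 3.36 = 232.1.
- Solving the two-proportion power formula (pooled variance under the null) for 80% power gives 16.50%, against 16.5% stated. All 27 cells of Table 2 agree to within 0.05 points.
- Planned detectable difference = 16.5 − 8 = 8.5 points.

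**3. Areas that refuse everything: selection**

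Suppose k equal-sized areas are randomised to an arm, one refuses, and its detection rate differs by d points from the mean of the others. The arm mean then moves by d/k. The three areas in appendix Section 4 are a minimum for enrolled areas, that is, after agreement. So one refusal that leaves three means k = 4. The values of d are assumptions.

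| d (points) | k = 4 | k = 6 |
|---|---|---|
| 2 | 0.5 | 0.3 |
| 4 | 1.0 | 0.7 |
| 8 | 2.0 | 1.3 |

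A more systematic pattern can be sketched, again by assumption. Let there be no true effect, let half the areas have high and half low baseline detection, averaging 8%, and let all UC areas agree. If a fraction r of the low-detection CI-CDS areas remains, the spurious difference is (high + r × low)/(1 + r) − 8.

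- 10%/6% split: r = 0.5 gives (10 + 3)/1.5 − 8 = 0.7 points; r = 0 gives 2.0 points.
- 12%/4% split: r = 0.5 gives (12 + 2)/1.5 − 8 = 1.3 points; r = 0 gives 4.0 points.

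**4. Areas that take the silent fallback: dilution**

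If a share s of CI-CDS patients is in silent-mode areas and is analysed as CI-CDS, the arm's expected rate is 8 + (1 − s) × 8.5. Power uses the effective sample size from step 2.

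| s (assumed) | CI-CDS rate | Power |
|---|---|---|
| 0 | 16.5% | 80% |
| 1/6 | 15.1% | 67% |
| 1/3 | 13.7% | 50% |
| 1/2 | 12.25% | 33% |

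Table 2 counts clinics, although service areas are randomised, so these power figures are illustrative only.

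**The case against.** The strongest reply is the fallback. A CI-CDS area that does not want the tool is not lost: it can run silently and still count as enrolled. Willingness to adopt the tool therefore does not by itself decide who is analysed. If every such area takes the fallback, selection through this route is zero and the cost is dilution, which pulls the result towards no effect. This stands, and it limits the point to areas that refuse even silent running.

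As-randomised analysis of silent-mode areas is also largely implied already, by the intent-to-treat attribution in Protocol Section 9.2.1 (main body) and the use of the same analytic approach at the replication site in Section 9.5.1. Refusal reporting may be in the unseen supplement. And Section 9.5.1 plans no pooled analysis and rests the effectiveness conclusion on the primary site. All of this stands too.

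A reader might infer from the minimum of three that one refusal removes a third of an arm, which would move the mean by 0.7, 1.3 or 2.7 points for the same assumed differences. The documents do not support that: three is a count of areas that have agreed, all eligible areas are randomised, and the number eligible is not given.

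What the reply does not remove is the route through outright refusal. An equal minimum commitment does not ensure equal refusal when one arm hears the heavier request first.

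**Conclusion.** The point holds in a limited form. Asking for participation after allocation, with an arm-specific first request, means that the enrolled replication arms are not guaranteed to have the similarity for which the appendix randomises. The selection risk comes only from areas that refuse everything (CI-CDS) or refuse silent running (UC). Areas that fall back to silent mode weaken the contrast without unbalancing it, provided they are analysed as CI-CDS.

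With four equal-sized areas randomised to an arm and one refusal, the shift is about 0.5 to 2.0 points against a planned detectable difference of 8.5 points, and smaller if more were randomised. This rests on assumed between-area differences of 2 to 8 points.

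A reader might go further and conclude that the replication comparison will be biased in favour of CI-CDS. The documents do not show this. They give no refusal rates or baseline rates by area, UC refusals could push the other way, and the larger shifts in the working require every low-detection CI-CDS area to refuse even silent running while every UC area agrees. The primary-site conclusion is unaffected.

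**What to change.** **Areas not yet told their arm.** Before allocation is generated or disclosed, obtain a signed MOU that commits the area to at least silent data collection and records its willingness to be offered the interface. An area that later declines the interface then still supplies data, so the selection route closes as long as that commitment is kept. The cost is moving a step that the appendix already includes. Some areas may decline at this stage, but a refusal before randomisation does not bias the comparison; it only narrows who is represented.

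**Areas already told their arm.** The documents do not state recruitment status, so this part may be the one that applies. In the site-specific supplement:

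- report by arm the numbers of service areas and clinics randomised, approached, fully implemented, silent-only and refused;
- give whatever baseline characteristics are available for each group (earlier diagnosis rates may not exist for areas that refused, since data come through the tool);
- confirm that silent-mode CI-CDS areas are analysed as CI-CDS;
- describe the replication comparison as open to post-randomisation selection.

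The cost is a participation table and a few sentences of text.

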9.4 Outcomes

9.4.2 Secondary Outcomes

Secondary Outcomes will not be assessed at the replication site and thus these procedures are not applicable.

10. DATA COLLECTION AND QUALITY ASSURANCE

The sole data source for the replication site is OCHIN EHR data. No claims-based data are available, nor will survey data be collected, at the replication site. The following EHR data will be collected from the CI-CDS tool and will be saved in an operational repository at HealthPartners. Individual and clinic identifying information, including patient name, date of birth, clinician name/ID, clinic name/ID, and department ID will then be removed from the data set and replaced by a random identifier prior to saving it into the research data repository.

Clinic-level data	Clinic name and/or ID, department ID, clinician name and/or ID
Patient-level data	Patient name (purged nightly), date of birth (purged nightly), age, gender, race, diagnosis (with dates), lab values (with dates), vitals (with dates), allergies (with dates), Rx (with dates), assessment results (with dates)
CI Wizard use data	Wizard print rates and click rates

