Replication: In addition to the primary effectiveness trial, the CI-CDS system will be implemented and evaluated at OCHIN, a network of safety net health centers clinics across the country. organized under a 501(c)(3) designation. Across the country, OCHIN's highly customized, centrally hosted EpicCare ambulatory system EHR is used in a broad network of primary care safety net settings including Federally Qualified Health Centers (FQHCs) and FQHC lookalikes, rural health centers (RHCs), school-based health centers, and county health departments. The replication site study design will be similar in that service areas with constituent primary care clinics will be randomized equally to a CI-CDS or UC treatment group. The CI-CDS system will be fully implemented in CI-CDS clinics and silently implemented in UC clinics (i.e., working in the background to collect data but not visible to clinicians). Patients will accrue into the study at index visits over a 6-month accrual period, with an approximately 6-month observation period for the last accrued patient, resulting in an ~12-month intervention period. See replication site-specific protocol details in **Section 15.5**.

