3.3 Study Enrollment Procedures

All primary care visits that take place at the randomized clinics after the CI-CDS system is implemented will be screened for intervention eligibility. The web platform in which the CI-CDS is housed is programmed to assess whether CDS content should be displayed each time the vitals section of the EHR is closed by extracting data elements from the EHR and supplying them to algorithms that assess eligibility. For the CI-CDS, this means that the algorithms run in all randomized clinics at all primary care visits. They confirm that the person is age-eligible, search for prior cognitive screening and assessment data, run the MC-PLUS algorithm to estimate risk of CI, and confirm that the patient does not already have a diagnosis of CI and that none of the exclusion criteria apply. In short, intervention eligibility is systematically assessed at all visits with all patients at the randomized clinics where CI-CDS is running. The platform documents all eligibility assessments (i.e., eligible and ineligible) so that the characteristics of visits and patients screened for eligibility can be quantified as each eligibility criterion is applied. Patients will be accrued into the study on the date of their first visit during the accrual period that meets all intervention eligibility criteria (i.e., index visit), and followed for the duration of the observation period.

We have received a waiver of informed consent for patients from the HealthPartners Institute Institutional Review Board (IRB) because the study is minimal or less than minimal risk compared to the risk associated with any primary care encounter. This was similarly granted for the R61 Phase. The evidence-based care recommendations in the CI-CDS intervention are from national guidelines and approved by primary and neurology care delivery leadership. Moreover, this pragmatic intervention could not be conducted if written informed consent were required to be obtained in the context of busy community-based primary care clinic environments. Note that patients who have requested non-participation in research studies will be excluded from all analyses.

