Step 3: Patient/Caregiver and Clinician Engagement at Primary Care Office Visits. At visits with patients with elevated CI risk or with identified CI-related care opportunities, the rooming staff receives an immediate BPA to print CDS engagement materials. Using this sequence of steps successfully implemented in previous studies, the rooming staff will print the materials from a link on the BPA and give the lay version to the patient/caregiver to review while waiting for the clinician. A professional version is provided to the clinician to review before entering the exam room. This approach has been well-liked by our clinicians to help them be prepared to engage patients in their care needs before the clinician-patient interaction.

Step 4. Online CDS for Clinicians with More Detail and Tools to Promote Efficiency. Clinicians can opt to view CDS and more detailed materials and tools online through an activity that is seamlessly integrated into the EHR and can be viewed in real time for any patient at any time they choose. Newer EHR features make it easier for the web-based application to be interactive with the end user. As the user interacts with the CDS interface, a summary is generated that captures patient CI risk or diagnosis, results of additional assessments completed, and actions recommended. This summary can then be copy and pasted into the clinician’s progress note. Our team includes very experienced EPIC programmers employed by our research institute who take full advantage of new functionality as it becomes available to make the CI-CDS interface and interactive features as efficient as possible for clinicians.

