## 2.4 Study Measures and outcome definitions

### 2.4.1 H1 outcome (primary): CI detection

The primary study outcome is CI detection. CI detection will be a binary outcome calculated from EHR data that is present if an ICD-10 diagnostic code for CI (dementia or mild cognitive impairment [MCI]) is documented at an outpatient or inpatient encounter, or added to the problem list, between the index visit and the end of the observation period, inclusive. The diagnostic codes that will denote CI detection will be the same as those used in determining eligibility (section 2.3.3). The data elements needed to calculate this outcome will be extracted at the conclusion of the observation period from the EHR of patients in the ITT population. It is hypothesized that patients in CI-CDS clinics will be more likely to have CI detected than patients in UC clinics.

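### At the replication site the only data route the protocol names is the tool's rooming-time exchange, which would miss CI diagnoses entered later unless another exchange follows; no end-of-observation extract is specified.

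*Protocol*

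**What the plan says.** **HealthPartners.** SAP 2.4.1 takes the H1 outcome from a single pull: the data elements "will be extracted at the conclusion of the observation period from the EHR of patients in the ITT population". Protocol 10.2 adds Clarity data to the tool's data for assessing CI diagnosis.

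**OCHIN.** Protocol appendix 15.5, section 10, says: "The sole data source for the replication site is OCHIN EHR data". It then says: "The following EHR data will be collected from the CI-CDS tool and will be saved in an operational repository at HealthPartners". The list that follows includes dated diagnoses. Appendix section 5.1 describes the transfer as OCHIN's "EHR securely exchanging data with the HealthPartners web service at every encounter of adult patients aged 65 or older", and says the tool will work much as it does at the primary site. Appendix section 7.2 uses the same source for safety: "Surveillance of information stored in the Wizard repository will be used to monitor safety events at the replication site". Appendix section 7.3.2 says emergency, hospital and death data are not available there, leaving suicide attempts as the one monitored event.

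**Trigger.** Protocol 3.3 says the platform runs "each time the vitals section of the EHR is closed by extracting data elements from the EHR". Protocol 5.1 (Step 1) and 6.2.1 put the trigger at blood-pressure entry by rooming staff. SAP 2.3.4 also places it in the rooming process.

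**Outcome and window.** Protocol 9.4.1 counts a CI code at an outpatient or inpatient encounter, or on the problem list, from the index date to the end of observation. Protocol 9.5.1 applies the same analysis at the replication site. Protocol section 2 gives a 6-month accrual there, "with an approximately 6-month observation period for the last accrued patient, resulting in an ~12-month intervention period".

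**The concern.** The tool is meant to prompt a diagnosis during the visit, but its data leave the EHR before the clinician enters the room. If those exchanges are the whole replication dataset, a diagnosis made at the index visit is absent from the index exchange. A diagnosis at a later visit is absent from that visit's exchange, and one made where no exchange fires is absent until the next one. The recorded outcome becomes CI diagnosed and visible at a later exchange, which is narrower than the H1 definition. A 6-to-12-month window leaves limited time for that later exchange.

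At stake are the replication's power, the size of its absolute effect, and whether its rates can be compared with those at HealthPartners. The suicide-attempt count shares the weakness: on this route an attempt after which the patient has no further exchange would not be recorded.

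**Working it through.** **1. Data routes side by side.**

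| | HealthPartners | OCHIN (appendix 15.5) |
|---|---|---|
| Source of diagnoses | EHR, plus Clarity (Protocol 10.2) | EHR fields collected from the tool (section 10) |
| When read | End of observation (SAP 2.4.1) | At encounters (section 5.1); trigger at rooming by analogy with Protocol 3.3, 5.1 and 6.2.1 |
| Final extract stated | Yes | No |
| H1 definition | Protocol 9.4.1 | Same, with no site-specific change |

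The route named for OCHIN does not by itself deliver the outcome defined for it.

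**2. Reproduce the plan's replication figure.** Inputs are from Protocol 9.2.2 and Table 2: 26 clinics, 60 patients per clinic, ICC 0.04, usual-care rate 8%, power 0.80, two-sided alpha 0.05.

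- Design effect = 1 + 59 × 0.04 = 3.36.
- Effective N = 1560 / 3.36 = 464.3, or n = 232.1 per arm.
- Power = Φ[(d − 1.96·s0)/s1], with d = p2 − p1, s0 = √(2·p̄(1−p̄)/n) and s1 = √([p1(1−p1) + p2(1−p2)]/n).
- At 8% versus 16.5%: d = 0.085, s0 = 0.03043, s1 = 0.03018, so power = Φ(0.840) = 0.80.

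This matches the stated 16.5%. All 27 cells of Table 2 reproduce to within 0.1 point. The table makes no allowance for missed diagnoses.

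**3. Apply an assumed capture share c, equal in both arms.** Observed rates are 8c and 16.5c. The ICC is held at 0.04, since Table 2 also applies one set of ICCs whatever the rate.

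| c | Observed rates | Difference (points) | Power |
|---|---|---|---|
| 1.0 | 8.0% vs 16.5% | 8.5 | 80% |
| 0.9 | 7.2% vs 14.85% | 7.65 | 75% |
| 0.8 | 6.4% vs 13.2% | 6.8 | 69% |
| 0.7 | 5.6% vs 11.55% | 5.95 | 63% |
| 0.6 | 4.8% vs 9.9% | 5.1 | 56% |
| 0.5 | 4.0% vs 8.25% | 4.25 | 48% |

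Worked line for c = 0.8: d = 0.068, s0 = 0.02760, s1 = 0.02742, Φ(0.507) = 0.69. The risk ratio stays at 16.5/8 = 2.06 in every row. Equal loss shrinks the absolute difference and the power, but it does not create an effect.

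**4. How far this depends on the ICC.** If misses were purely random with the same c in every clinic, the ICC would also shrink, to 0.04 × c(1−p)/(1−cp). With p = 12.25% (the mean of the two rates):

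- c = 0.8: ICC 0.0311, design effect 2.837, n = 275.0 per arm, power about 77%.
- c = 0.7: ICC 0.0269, design effect 2.586, n = 301.7 per arm, power about 74%.

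If clinics differ in how often patients return, capture itself varies by clinic and pushes the ICC back up. So 69% and 63% follow the plan's own convention, and 77% and 74% are the milder case.

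**The case against.** **The SAP defers this point.** SAP 2.1 says outcome measurement at the replication site will be set out in a site-specific supplemental plan, which is not among the documents. This stands. The finding is about what the current protocol names, and the supplement may close the gap.

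**Loss without another visit is an inference.** The appendix speaks of every encounter and takes the vitals trigger from the main protocol. Vitals closed twice in one visit would send data again. Diagnoses carry dates, so an exchange after the window could reveal one made inside it. The Clarity supplement is not expressly withdrawn for OCHIN. All of this stands, and is why the wording is conditional. But the appendix gives no data-cut date, no post-window run and no second source.

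**A reader might infer bias towards the intervention.** Clinicians in CI-CDS clinics have an interface that "can be viewed in real time for any patient at any time they choose", and the tool prompts follow-up, so more exchanges might occur there. The documents do not establish this. They do not say that viewing sends new data, and the sample screens in Protocol 15.4 show data refreshed 85 days earlier. Protocol 5.1 and SAP 2.1 say collection is identical across groups. Extra follow-up visits in one arm remain possible, but any figure for a spurious effect would simply reflect the assumed gap in exchanges. Nor do the documents describe a typical OCHIN visit pattern.

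**The consequence is limited.** Protocol 9.5.1 rests the effectiveness conclusion on the primary site and plans no pooling. This stands.

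**Conclusion.** The concern holds in a conditional form. As written, the one data route named for OCHIN is read at rooming, and it would under-capture the H1 outcome that the protocol carries over to that site. The size is unknown because the documents give no capture rate. With equal capture assumed, 26 clinics and ICC 0.04, power for 8% versus 16.5% would be about 69% at 80% capture and 63% at 70%, or about 77% and 74% if misses are purely random across clinics. These figures take the plan's 80% starting point as given.

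Different capture by arm is a possibility to check, not a finding. The trial's primary conclusion is not affected. The replication estimate should not rest on this route without either a final extract or a relabelled outcome.

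**What to change.** In appendix 15.5, section 10, and in the site-specific supplemental plan, state that the replication H1 outcome comes from one OCHIN EHR query of encounter diagnoses and problem list. Run it after observation ends, identically for every accrued patient in both arms. Take suicide-attempt codes from the same query if they are available. Keep tool data for eligibility, index date and use metrics.

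Settle linkage first. Protocol 5.1 (Step 1) says a study ID is saved in the EHR, but appendix section 10 purges names and birth dates nightly and replaces identifiers before research storage. Confirm that the study ID works at OCHIN before those identifiers are gone.

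The cost is one data pull, its linkage arrangement at OCHIN and an appendix amendment; no patients or visits are added.

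If OCHIN cannot supply the query:

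- use only automatically triggered exchanges, in both arms;
- keep the silent exchange running past the window, and count diagnoses dated within it;
- report by arm the share of patients with an exchange after index;
- describe the replication outcome as CI diagnosis visible at a later tool exchange.
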